### Open Interview

Following the Follow-Up Pain Questionnaire & Present Mood Questionnaire, participants will be asked to provide any feedback they had from the VR treatment and to describe their experiences throughout the experiment. Was the treatment comfortable? Do they think it could help them manage pain? The interview will be left in an open format to allow participants more freedom in expressing themselves.

### Cleaning of VR Headset

After each study visit with a patient, research personnel will wipe down the face cushion and the plastic exterior of the VR headset using a PDI Sani Cloth Plus Germicidal Wipe. This is the sanitization procedure recommended by the Infection Control Preventionist at DSMC.

### Collecting Data from Medical Records

After completion of the study visit, research personnel will collect data from the patient's medical records if the patient completes and signs the HIPAA Research Authorization form. All PHI obtained from medical records (self-report pain ratings, medication information (names, doses, and timing), hospital room number, phone number, email address, date of birth, diagnosis information, and medical progress notes) will be accessed electronically by research personnel on a Seton computer at the hospital. Electronic data from medical records will be entered directly into a password protected tracking sheet on UT Box and maintained by research personnel.

### One-week E-mail Follow-up

One-week after participating in the experiment participants will be e-mailed a series of follow-up questionnaires that will include the Follow-Up Pain Questionnaire, Present Mood Questionnaire, and Participant Satisfaction Survey. If participants cannot be reached by email, research personnel will contact them via telephone or a follow-up in person interview.

## Hospital Study Visit Overview

1. Obtain Informed Consent
2. Baseline Assessment (15 minutes)
  - a. Assess consciousness
    - i. Glasgow Coma Scale
    - ii. Mini Mental Status Exam
  - b. Demographic Questionnaire
  - c. Media Use Survey
  - d. Personal Health Questionnaire-8
  - e. Pre-Treatment Pain Questionnaire
  - f. Present Mood Questionnaire
3. Treatment Conditions
  - a. Film VR condition (30 minutes)
    - i. Samsung Gear VR information session
      1. Participants will receive information describing the Gear VR and instructed to fully engage with the VR video.
    - ii. Samsung Gear VR Fitting
      1. Gear VR will be adjusted to participant's head
    - iii. Watch 9 minute 360° 3D HD VVR film
    - iv. Administer Post-Treatment Assessments (5-10 minutes)
      1. Post-Treatment Pain Questionnaire
      2. Present Mood Questionnaire
      3. Presence Inventory
      4. Absorption Survey
      5. Attitudes Toward the Experience Survey
      6. Human Presence Survey
      7. Location Familiarity Survey
    - v. Wait 10 minutes
    - vi. Administer both the Follow-Up Pain Questionnaire & Present Mood Questionnaire (3-5 minutes)

## Research Proposal

---

- b. Animated VR condition (30 minutes)
    - i. Samsung Gear VR information session
      1. Participants will receive information describing the Gear VR and instructed to fully engage with the VR video.
    - ii. Samsung Gear VR Fitting
      1. Gear VR will be adjusted to participant's head
    - iii. Watch 9-minute animated film
    - iv. Administer Post-Treatment Assessments (5-10 minutes)
      1. Post-Treatment Pain Questionnaire
      2. Present Mood Questionnaire
      3. Presence Inventory
      4. Absorption Survey
      5. Attitudes Toward the Experience Survey
      6. Human Presence Survey
      7. Location Familiarity Survey
    - v. Wait 10 minutes
    - vi. Administer both the Follow-Up Pain Questionnaire and Present Mood Questionnaire (3-5 minutes)
  - c. Waitlist condition
    - i. Participants will be directed to wait patiently for 9 minutes
    - ii. Administer both the Follow-Up Pain Questionnaire & Present Mood Questionnaire (3-5 minutes)
    - iii. Participants can choose to watch one of the two treatment VR videos for 9 minutes.
      1. Administer Post-Treatment Pain Questionnaire
4. Open Interview (3-5 minutes)
  5. One-week e-mail follow-up (10-15 minutes)
    - a. Follow-Up Pain Questionnaire
    - b. Present Mood Questionnaire
    - c. Participant Satisfaction Survey

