### Conditions

Participants will be randomized to the 360° 3D HD video VR film condition, animated video VR condition, or waitlist condition. Those randomized to the waitlist group will complete all study procedures except the VR exposure. After completion of the study visit, we will give those in the waitlist condition the option of experiencing the 9-minute VR video of their choosing.

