### Post-Treatment Assessments

Following the 9 minutes of VR exposure or waiting, participants in each condition will complete post-treatment assessments for 5-10 minutes. These assessments will measure pain, presence, mood, negative effects of VR, absorption, human presence, participant's prior familiarity with the locations depicted in the VR video, and their attitude toward the VR session immediately after the treatment. Nausea, dizziness, eyestrain, and head pain is being assessed in an effort to identify the incidence of this component of simulator sickness sometimes associated with VR use (Kennedy et al., 1992). Following the Post-Treatment assessments, the Follow-Up Pain Questionnaire & Present Mood Questionnaire will be administered 10 minutes following the treatment. These follow-up assessments are in place in order to track the lasting pain reduction from the VR treatments.

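### The visit overview contradicts the narrative on the waitlist's pain forms; followed as written, no in-visit pain form after baseline matches the VR arms in both wording and timing

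*Protocol*

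**What the plan says.** The narrative in section 4 describes a matched schedule. Under Conditions: "Those randomized to the waitlist group will complete all study procedures except the VR exposure". The same paragraph places the waitlist's VR outside the visit: "After completion of the study visit, we will give those in the waitlist condition the option". Under Post-Treatment Assessments: "Following the 9 minutes of VR exposure or waiting, participants in each condition will complete post-treatment assessments for 5-10 minutes". Pain is among the things measured there. The Follow-Up pain and mood forms then come 10 minutes after treatment, with no exception by arm, to track how long the pain reduction from VR lasts.

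The Hospital Study Visit Overview sets out something else. For each VR arm (3.a and 3.b), the video is followed by "Administer Post-Treatment Assessments (5-10 minutes", which includes the Post-Treatment Pain Questionnaire. A 10-minute wait comes next, and then the Follow-Up forms. For the waitlist (3.c) the steps are "Participants will be directed to wait patiently for 9 minutes", then "Administer both the Follow-Up Pain Questionnaire & Present Mood Questionnaire (3-5 minutes", then "Participants can choose to watch one of the two treatment VR videos for 9 minutes". The waitlist's only Post-Treatment pain form sits under that last, optional step, ahead of the Open Interview (item 4).

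Section 5 (Measures) describes the two forms as having the same items. The Post-Treatment version asks about pain during the VR, and the Follow-Up version asks about the last 10 minutes. The Assessment Schedule table has a single after-treatment column, not split by arm. The Follow-Up entry in section 5 counts four follow-up pain assessments, whereas the overview has one in the visit and one at one week.

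**The concern.** Staff have two incompatible schedules for the control arm, which differ on three points: which pain form the waitlist completes after its wait, when it completes the Follow-Up form, and whether its optional VR falls inside the visit or after it. The hypothesis at the end of section 3 sets film VR against both animated VR and the waitlist, so one of the two hypothesised contrasts depends on this arm.

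Under the overview, a film-waitlist comparison straight after the video or wait mixes the VR effect with a difference in wording. A comparison on the Follow-Up form mixes it with elapsed time. The waitlist then offers no in-visit control for lasting relief. If some staff follow the narrative and others the overview, timing also varies within the waitlist arm. This is a matter of data collection: no later analysis can recover a rating that was not taken at the matching time.

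**Working it through.** No figure in the protocol needs reproducing, so the check compares the schedules using the stated durations. Let t = 0 be the end of the 9-minute video or wait, in minutes.

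**Time of the Follow-Up form**
- VR arms, overview read in sequence: battery of 5 to 10, then a wait of 10, so t = 5 + 10 = 15 to 10 + 10 = 20.
- VR arms, narrative: t = 10.
- Waitlist, overview: straight after the wait, t = 0.
- Discrepancy: 15 to 20, or 10 if the VR arms follow the narrative.

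**Recall windows**

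| Comparison | VR arms | Waitlist (overview) | Shared minutes |
|---|---|---|---|
| Follow-Up form, VR arms at t = 10 | 0 to 10 | -10 to 0 | 0 |
| Follow-Up form, VR arms at t = 15 | 5 to 15 | -10 to 0 | 0 |
| Follow-Up form, VR arms at t = 20 | 10 to 20 | -10 to 0 | 0 |
| Forms given at t = 0 | -9 to 0, asked as pain during VR | -10 to 0, asked as the last 10 minutes | 9 |

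On the Follow-Up form the waitlist rates the wait itself, while the VR arms rate a period after the video. At t = 0 the items and nearly all the minutes agree, but the wording depends on arm. The waitlist's Post-Treatment form comes only after its own VR, and only in patients who choose it.

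The narrative cannot simply be applied instead, because the Post-Treatment form is worded for someone who has had VR.

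**Which follow-up time fits the stated block.** The overview heads the film arm "Film VR condition (30 minutes", and the animated arm has the same length.
- Sequential reading: 9 + 5 + 10 + 3 = 27 to 9 + 10 + 10 + 5 = 34, before instruction and fitting.
- Follow-up at t = 10, with the battery inside those 10 minutes: 9 + 10 + 3 = 22 to 9 + 10 + 5 = 24, leaving 6 to 8 for instruction and fitting.

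**Sensitivity, under assumption only.** Suppose wording or timing alone shifts the film-waitlist difference by b standard deviations and VR has no true effect. With 67 per arm and a two-sided 5% t-test, df = 132 and the noncentrality parameter is b × √(67/2).
- b = 0.1: rejection probability 0.089
- b = 0.2: 0.210
- b = 0.3: 0.407

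These values of b are not in the protocol. They show how sensitive the test would be and do not estimate the bias.

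**The case against.** The best defence is that the overview's waitlist form is a deliberate counterpart. A patient who only waited cannot rate pain during VR, so the same items are asked about the last 10 minutes, and a usable change from baseline at t = 0 survives. Much of this stands: the remaining difference at t = 0 is one of wording. The forms themselves are not shown, and section 5 also says the Post-Treatment form covers pain following VR, so some item may be free of the recall phrase. Confounding by wording is therefore possible but not demonstrated. The Present Mood Questionnaire is already given at about t = 0 in all three arms.

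It can also be said that the hypothesis names no time point, and that an analysis plan might not compare the Follow-Up form with the waitlist. That limits the consequence but leaves the contradiction in place, and the in-visit follow-up comparison would still be lost.

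Two further points are fair. One-week waitlist values may follow VR under either schedule, so that weakness does not come from this contradiction. And even at a common follow-up time, the VR arms would spend part of the recall window on a longer battery than the waitlist, so a difference in activity would remain.

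**Conclusion.** The concern holds. The overview contradicts the Conditions and Post-Treatment Assessments text on the waitlist's forms, their timing and its optional VR, and neither the Assessment Schedule table nor section 5 settles it. Followed as written, the overview gives waitlist and VR arms no in-visit pain form after baseline that agrees in both wording and time. The Follow-Up recall windows share 0 of 10 minutes on either reading. The nearest pairing, at t = 0, shares 9 minutes but not the wording.

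This rests on the overview being followed and on the recall wording being as section 5 describes. The size and sign of any bias are unknown. Film versus animated is unaffected, because those two schedules are identical, and the baseline and one-week forms are common to all arms. It must be fixed because it bears on a hypothesised contrast and cannot be repaired at analysis.

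**What to change.** 1. Straight after the video or wait, give all three arms the same pain items with one neutral window, for example the last 9 minutes. Keep the mood form there, as now.
2. Give the Follow-Up pain and mood forms at one fixed time after the end of the video or wait in every arm. The narrative's 10 minutes fits the 30-minute VR block; the sequential reading does not fit once instruction and fitting are added.
3. Offer waitlist VR only after both sets of forms. Keep any form completed after it out of the between-arm comparison, record who took VR, and state that one-week waitlist values may follow VR. Acknowledge the longer VR-arm battery as a remaining difference.
4. Make Conditions, Post-Treatment Assessments, the Visit Overview, the Assessment Schedule table and the two form descriptions in section 5 agree, including 10 versus 15 to 20 minutes and the count of four follow-up assessments.

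The cost is a protocol and form amendment plus waitlist time, with no extra patients or staff. At t = 10 the added time is 67 × 10/60 = 11.2 hours in total; at t = 20 it is 67 × 20/60 = 22.3 hours. Timed waitlist steps (baseline, wait, forms, interview) are now 15 + 9 + 3 + 3 = 30 to 15 + 9 + 5 + 5 = 34 minutes. They become 40 to 44 at t = 10, or 50 to 54 at t = 20. Optional VR and its form (assumed 3 to 5 minutes) add 12 to 14, giving 52 to 58 or 62 to 68, before consent, instruction and fitting. If that VR is counted in the visit, the stated hour is tight at t = 10 and exceeded at t = 20.

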## Research Proposal

---

### b. Resources

The project is funded internally through the Longhorn Innovation Fund for Technology (LIFT Grant).

[name] will be our Seton PI and resource for running the study at University Medical Center Brackenridge and Dell Seton Medical Center. [name] is the Vice President of Medical Affairs and Medical Director, Dell Seton Medical Center at the University of Texas and University Medical Center Brackenridge. Through the hospital he is donating the time of the hospital staff and the VR headset (Galaxy phone with Samsung Gear VR). [name] will have access to identifiers and will also aide in recruitment as described in the recruitment section (page 14, Section 6, part "e"). [name] will not directly recruit participants for the study.

### c. Study Timeline

## Research Proposal

---

Data collection will begin once IRB approval has been granted (tentatively November 2016) and has an anticipated end date of August 2017. Results will be disseminated by September 2017.

### 5. Measures

Assessments will be collected as outlined in the table below

Table. Assessment Schedule		Study Visit Before Treatment	Study Visit After Treatment	1-Week Follow-Up
Assessments				
Glasgow Coma Scale		X		
Abbreviated Mini Mental Status Exam		X		
Demographics Questionnaire		X		
Media Use Survey		X		
Personal Health Questionnaire-8		X		
Pre-Treatment Pain Questionnaire		X		
Present Mood Questionnaire		X	X	X
Post-Treatment Pain Questionnaire			X	
Presence Inventory			X	
Absorption Survey			X	
Attitudes Toward the Experience Survey			X	
Human Presence Survey			X	
Location Familiarity Survey			X	
Follow-Up Pain Questionnaire			X	X
Open Interview			X	
Patient Satisfaction Survey				X

- Glasgow Coma Scale (GCS) (Teasdale & Jennett, 1974)

The Glasgow Coma Scale (GCS) (Teasdale & Jennett, 1974) is a commonly used instrument in clinical practice and provides a structured method for assessment of the level of consciousness. The GCS has good reliability and well-established cross-sectional construct validity (Prasad, 1996).

- Mini Mental Status Exam (MMSE) (Folstein, Folstein, & McHugh, 1975)

The Mini Mental Status Exam (Folstein et al., 1975) is a questionnaire used extensively in clinical and research settings to measure cognitive impairment. We will be using an abbreviated version in combination with the GCS to assess for adequate consciousness for participation in the study.

- Demographics Questionnaire

## Research Proposal

---

Participants will be asked to provide standard demographic information (i.e. age, gender, race/ethnicity, level of education, etc.). Participants will also be asked about hearing and visual impairment as well as their history of motion sickness.

- **Media Use Survey**

The Media Use Survey is a brief 4-question survey aimed to determine the participant's typical prior use of TV, online videos, and video games. The measure also asks about prior use of a virtual reality headset.

- **Personal Health Questionnaire-8 (PHQ-8)**

The Patient Health Questionnaire 8-Item (PHQ-8) is a brief self-report measure of major depressive disorder (Koneke, Spitzer, & Williams, 2001). The PHQ-8 is considered to be a valid measure of depression for population-based studies and clinical populations (Kroenke et al., 2009), with a cut off score of equal to or greater than 10 considered diagnostic for current depression. The PHQ-8 is derived from the PHQ-9 by removing the last question regarding suicidality.

- **Pre-Treatment Pain Questionnaire**

The Pre-Treatment Pain Questionnaire will be used to assess the participant's pain prior to receiving VR treatment. It is derived from the Brief Pain Inventory (BPI; Cleeland and Ryan, 1994; Cleeland et al., 1996) and contains Numerical Rating Scales (NRS) aimed at assessing the participant's pain intensity, pain quality, pain interference, and pain relief, as recommended by the IMMPACT recommendations for outcome measures in clinical pain trials (Dworkin et al., 2005). The NRS is one of the most common measures for assessing pain, and has been a validated outcome measure of pain intensity (Breivik, Björnsson, & Skovlund, 2000; Breivik et al., 2008). The NRS was also chosen because it could be administered orally if patients cannot use their hands to write or use the iPad.

- **Present Mood Questionnaire**

The Present Mood Questionnaire will be used to assess the participant's current mood. The survey uses a labeled (0-10) NRS to measure the extent that the participant feels sad, anxious, happy, and tranquil.

- **Post-Treatment Pain Questionnaire**

The Post-Treatment Questionnaire will be used to assess the participant's pain during and following the virtual reality treatment. The NRS pain assessment questions are identical to the Pre-Treatment Pain Questionnaire, except questions are altered to specify pain the participant experienced during the VR treatment.

- **Presence Inventory**

The Presence Inventory is adapted from The ITC-Sense of Presence Inventory (Lessiter et al., 2001) and The Igroup Presence Questionnaire (IPQ). It will be used to assess the degree of Spatial Presence (The ITC-Sense of Presence Inventory), Ecological Validity (The ITC-Sense of Presence Inventory & IPQ), and Negative Effects (The ITC-Sense of Presence Inventory).

## Research Proposal

---

- *Absorption Survey (adapted from Agarwal, & Karahanna, 2000)*

The Absorption Survey (adapted from Agarwal, & Karahanna, 2000) is a 12-item NRS that will be used to measure participant engagement with the virtual world. Participants rate the degree to which they agree with the statements on a 1-10 scale, with 0 being “strongly disagree” and 10 being “strongly agree”.

- *Attitudes Toward the Experience Survey (adapted from Sundar, 2000)*

The Attitudes Toward the Experience Survey (adapted from Sudnar, 2000) is a 12-item NRS that will be used to measure the participant’s attitude toward the VR experience. Participants rate the degree to which they agree with the statements on a 1-10 scale, with 0 being “strongly disagree” and 10 being “strongly agree”.

- *Human Presence Survey (adapted from Basdogan, Ho, Srinivasan, & Slater, 2000)*

The Human Presence Survey (adapted from Basdogan, Ho, Srinivasan, & Slater, 2000) is a 2-item measure that will be used to assess the extent that participants felt they were with other people during the VR session.

- *Location Familiarity Survey*

The Location Familiarity Survey is a 1-item measure that will be used to assess the participant’s prior familiarity with the locations depicted in the virtual reality videos.

- *Follow-Up Pain Questionnaire*

The Follow-Up Questionnaire will be used to measure the participant’s pain in the 4 follow-up pain assessments following the VR treatment. It will also be administered during the 1-week follow-up survey. It is identical to the Post-Treatment Pain Questionnaire, but asks for pain ratings during the last 10 minutes instead of during the VR session.

- *Open Interview*

The Open Interview will be comprised of brief open-ended questions designed to collect general patient feedback regarding their thoughts about the virtual reality treatment upon conclusion of the study visit. It will be used to guide future research methods.

- *Patient Satisfaction Survey*

The participant satisfaction survey will be used to assess participant acceptability and satisfaction of the virtual reality treatment 1-week following completion of the study. It has both questions utilizing a Numeric Rating Scale as well as open-ended questions and will be used to guide future research methods. The survey will also include the Patient Global Impression of Change scale (PGIC; Guy, 1976). This measure is a single-item rating by participants of their improvement with treatment during a clinical trial on a 7-point scale that ranges from “much better” to “much worse” with “no change” as the mid-point. There has been widespread use of the PGIC in recent clinical pain trials (e.g. Dunkl et al., 2000; Farrar et al., 2001) and the data provide a responsive and readily

## Research Proposal

---

interpretable measure of participants' assessments of clinical importance of their improvement or worsening over the course of a clinical trial (Dworkin et al., 2005).

### 6. Participants

#### a. Target Population

Our target enrollment is 201 participants who complete all study procedures. We will recruit 500 participants 18 years of age and older in order to enroll 201 participants to account for dropouts and ineligible participants. Participants will be patients experiencing current pain that is not related to day-to-day, normal experiences (such as minor headaches, sprains, and toothaches) at University Medical Center Brackenridge or Dell Seton Medical Center in Austin, TX, or Baylor Scott & White Medical Center Temple in Temple, TX, that are referred to the study by hospital staff.

The final number of participants enrolled in each of the three study conditions is expected to be 67 participants.

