Our team has been working with virtual reality for 10 years now conducting several large randomized controlled trials (Powers & Emmelkamp, 2008; Meyerbröker, Powers, van Stegeren, & Emmelkamp, 2012; Powers et al., 2013; Tart et al., 2013). Two major recent innovations are central to this proposal. First, the realism possible in VR has dramatically increased with the use of 360-degree 3D HD film environments. 360-Degree Video VR is a radical filmmaking technology that can turn live action footage into a 360-degree environment that users can interact with. 360-Degree Video VR is made by filming with an array of multiple HD cameras carefully arranged to capture all angles in a 360-degree area of a live action event (see Figure 3). Then those angles are stitched together in post-production into a 360-degree texture sphere and the sphere is then mapped to the head tracker on the users HDM. Leading to the effect that when a user turns his head, their view of the live action video footage turns with them in real time (e.g. if the user looks down, the camera pans down and the user sees the floor) allowing the user to look around anywhere in the 360 degrees of filmed footage of the live action event. The benefit of 360-Degree Video VR as opposed to CGI VR is that it is photo realistic, does not suffer from the uncanny valley effect of CGI, and is able to capture nuances of real life fears that are hard to reproduce with CGI. In addition, the projected cost of the end product is approximately \$500. This enhanced level of immersion has the potential to dramatically improve the efficacy to reduce acute and chronic pain (see above). Second, deployment of the resulting content to patients is now much smaller and inexpensive (e.g., \$99 for a Samsung Galaxy Gear VR (see Figure 4) or \$20 for Google Cardboard systems). This technology makes VR accessible to anyone with a smartphone.

The current study seeks to test the efficacy of the standard animated/CGI VR versus the enhanced 360-degree 3D HD film versions of VR in reducing pain in hospital patients. To this aim we will enroll 201 adult participants experiencing pain University Medical Center Brackenridge (UMCB), Dell Seton Medical Center (DSMC), Baylor Scott & White Medical Center Temple (BSWMCT), and randomly assign them to the enhanced (360-Degree Video VR) film condition ( $n = 67$ ), the standard (animated/CGI film) condition ( $n = 67$ ), or the waitlist

Figure 3. 360-degree

Figure 4. New affordable delivery

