## Research Proposal

---

condition ( $n = 67$ ). We anticipate we will need to recruit and consent a total of 500 participants due to the anticipated number of screen failures (due to inclusion/exclusion criteria). We hypothesize that the film VR will show greater pain reductions and increased functioning relative to both the animated VR and the waitlist condition.

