### Treatment

Following the acquisition of consent and the baseline assessments, participants will be outfitted with a Samsung Gear VR headset. Before the headset is placed on the patient's head, the patient will be given the option to wear a plastic shower cap over their head for the headset straps to rest on. This was recommended by the Infection Control Preventionist at DSMC. The shower cap is not required if the patient does not desire to wear one. The research assistant will help them adjust the headset. If the participants record any discomfort, the research assistant will attempt to adjust the settings on the Samsung Gear VR. If the participant finds that regardless of the settings, they cannot watch the video comfortably, they will be thanked for their time and their participation in the study will end.

After the headset is properly calibrated, the participant will receive instructions that they are about to view VR footage of central Texas locations. At the same time, they will be told that during the task they should try to imagine that they are actually at the location experiencing the scenery first hand. Additionally, participants will be instructed not to exert their body in any capacity that may cause additional pain while experiencing the virtual environment. They will be instructed that if at any time they become uncomfortable or wish to stop using the Gear VR, they may do so at anytime. Before watching the video, patients will be outfitted with a pair of headphones. The headphone ear cushions will be covered with sanitary disposable headphone covers. The covers on each ear cushion will be disposed of in a hospital trash can after each patient is finished watching the VR video.

Participants in the enhanced film condition will view 9 minutes of VR film footage of representative Austin scenes. The 9 minutes of footage will be alternating 30 second clips of Hamilton Pool Preserve in Dripping Springs, TX, a rower on Lady Bird Lake in Austin, TX, Red Bud Isle in Austin, TX, and Zilker Botanical Gardens in Austin, TX. These locations were picked for their beauty and likeliness for participants to be immersed in and distracted by the aesthetically pleasing footage.

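### The protocol uses 201 (67 per arm) both for patients randomised and for patients completing everything, and its headset exit rule loses post-treatment pain data in the two VR arms only

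*Protocol*

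**What the plan says.** **Number randomised.** The last paragraph of section 3 (Purpose) states: "To this aim we will enroll 201 adult participants experiencing pain". It continues "randomly assign them to the enhanced (360-Degree Video VR) film condition ( $n = 67", with the same number for the animated arm ("the standard (animated/CGI film) condition ( $n = 67") and for the waitlist. Here 201 counts patients at assignment.

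**Number completing.** Section 6a (Target Population) opens: "Our target enrollment is 201 participants who complete all study procedures". It closes: "The final number of participants enrolled in each of the three study conditions is expected to be 67 participants". So one short section describes the target first as completers and then as enrolled patients. By the visit overview in section 4, the full set of procedures includes the one-week questionnaires.

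**The 500.** Section 3 explains it by ineligibility alone: "recruit and consent a total of 500 participants due to the anticipated number of screen failures (due to inclusion/exclusion criteria". Section 6a says that the same 500 covers dropout as well as ineligibility.

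**The exit rule.** Section 4 (Treatment) says of a patient who cannot be made comfortable with the video, whatever adjustment is tried: "they will be thanked for their time and their participation in the study will end". The Hospital Study Visit Overview lists headset fitting as a step within the film and animated conditions. Waitlist patients are offered a video only after their own waiting-period assessment.

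**The concern.** A sample-size target has to say what it counts. If 201 is the number randomised, fewer than 67 per arm will supply complete data. If it is the number completing, more than 201 must be randomised, and the protocol gives neither that larger number nor a loss rate from which to derive it. The team could not tell from this text when enrolment is finished.

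The exit rule makes this more than a labelling problem. It removes patients for a reason tied to the assigned treatment, and it also ends their data collection. Patients who cannot tolerate the headset contribute no post-treatment pain score if assigned to VR. Similar patients assigned to waitlist do contribute one. Section 3 names film VR versus waitlist as part of the main hypothesis, and that is the contrast most exposed.

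**Working it through.** **1. Reproducing the stated figure.** 3 × 67 = 201 exactly, under either meaning, so the arithmetic does not show which one is intended. The protocol states no alpha, power, effect size, SD or dropout rate, so 201 cannot be checked against a power formula.

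**2. How far apart the two meanings are.** For a loss d after randomisation, equal in all arms, a completer target of 201 needs 201/(1 − d) randomised, and 201 randomised gives 201 × (1 − d) completers. The values of d are assumptions.

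| Assumed d | To randomise for 201 completers | Completers from 201 randomised |
|---|---|---|
| 0% | 201 | 201 |
| 5% | 212 | 191 |
| 10% | 224 | 181 |
| 15% | 237 | 171 |
| 20% | 252 | 161 |

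The meanings coincide only in the first row. At 5–20% they differ by 11 to 51 patients to randomise, or by 10 to 40 completers. All these totals fit within the 500, so either target is feasible alone, but one figure of 201 cannot serve as both.

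**3. Where the exit falls.** Section 4 (Treatment) ends participation at headset adjustment. The visit overview puts that adjustment inside the two VR conditions, hence after assignment. The waitlist has no headset step before its comparison data are collected. The exit therefore removes in-visit pain data from two arms and not from the third.

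**4. In-visit pain data if 201 is the number randomised.** The only related figure is in section 6d (Risks): fewer than 10% had cyber-sickness symptoms with older equipment, and fewer are expected here. That is a symptom rate, not an exit rate. I assume a 3–10% exit, with 10% as an upper-end value.

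- 3%: 67 × 0.97 = 65.0 per VR arm
- 10%: 67 × 0.90 = 60.3 per VR arm
- Waitlist: 67, as this exit does not apply

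**5. Effect on precision between the VR arms.** I assume a two-sided 5% test, 80% power and two equal groups. The detectable difference in SD units is approximately (1.96 + 0.84) × √(2/n), and the t distribution adds about 0.004.

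| n per VR arm | Normal approximation | With t distribution |
|---|---|---|
| 67 | 0.484 | 0.488 |
| 65 | 0.491 | 0.495 |
| 60 | 0.512 | 0.516 |

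The move is from 0.49 to about 0.50–0.52 SD.

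**6. One-week outcomes.** Questionnaire non-response adds to the loss here, in every arm. With an assumed 20% non-response on top of a 10% exit:

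- Each VR arm keeps 67 × 0.90 × 0.80 = 48.2, with a detectable difference of about 0.58 SD.
- The waitlist keeps 67 × 0.80 = 53.6.
- To reach 67 full completers per arm, each VR arm needs 67/(0.90 × 0.80) = 93.1, so 94, and the waitlist needs 67/0.80 = 83.8, so 84. The total is 94 + 94 + 84 = 272.
- Over 3–10% exit and 10–30% non-response, that total runs from 77 + 77 + 75 = 229 to 107 + 107 + 96 = 310.

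**The case against.** **Sizing for completers is ordinary.** Randomising more people so that a planned number finish is normal dropout inflation. Selection arises only if those who leave are then replaced or dropped from the analysis. The protocol says neither, and the analysis set may properly be left to an SAP that is not shown. This stands, so the bias has to be stated as conditional. A reader might infer that the trial recruits until 67 headset-tolerant patients per VR arm have finished; the documents do not say so.

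**The SAP can settle it.** Only in part. An SAP can define who is analysed, but it cannot recover study questionnaires that were never given because participation had ended. Chart pain ratings might exist for patients who authorised access, but the protocol does not tie them to the visit's assessment times.

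**Timing is inferred.** The protocol does not state when randomisation occurs. Its placement before fitting rests on the visit overview. That is the natural reading, but it is an inference.

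**Not every interruption is an exit.** Stopping the video part-way is described separately from being unable to watch at all, and nothing says that such a patient's assessments are skipped. The exit rate should cover only the latter.

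**The waitlist also loses patients.** It does, at one week. The one-sided loss concerns this exit and the in-visit scores, so it would be wrong to say that the waitlist keeps everyone.

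**201 need not mean randomised.** Correct. A completer target with a stated larger number to randomise would resolve the contradiction equally well.

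**Conclusion.** The contradiction is established from the text. 201 is the number randomised in section 3 and the number completing in section 6a, both cannot hold once anyone is lost, and the two sections give different reasons for the 500. The exit rule, read with the visit overview, leaves post-treatment pain data missing in the VR arms only. This can bias VR versus waitlist if those patients are replaced or omitted, and film versus animated only if the two videos differ in tolerability.

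The loss of precision is small: about 60–65 per VR arm for in-visit pain and a detectable difference of about 0.50–0.52 SD instead of 0.49, on an assumed 3–10% exit. No stated power calculation is invalidated, because none is given.

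Two stronger readings are not supported. A reader might quote 0.58 SD as the trial's detectable difference. That figure rests mainly on an assumed 20% one-week non-response, which does not touch in-visit pain, so it applies only to one-week outcomes or an analysis of full completers. A reader might also say that VR relief would be overstated by about 11% (1/0.90 = 1.11). That needs a completer analysis, the top assumed exit rate and no relief at all in everyone who exits.

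**What to change.** 1. Use one definition of 201 in sections 3 and 6a. The preferable one is the number randomised, 67 per arm, with no replacement after randomisation. Give expected completers as a separate, smaller figure with the assumed loss rate.
2. If 201 is kept as the completer target, state the larger number to randomise and the loss rates behind it, and keep every randomised patient in the count.
3. Give one reason for the 500 in both sections, saying whether it covers dropout after randomisation or ineligibility only.
4. Amend section 4 (Treatment) so that being unable to use the headset ends the viewing but not data collection. Ask willing patients for the in-visit and one-week pain forms and keep them in their assigned arm. The Follow-Up Pain Questionnaire asks about the preceding ten minutes, so it can be answered without having watched the video. This changes nothing about when a patient may stop.

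The cost is protocol wording, a few extra questionnaires from patients already in the room, and a less favourable completer figure.
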